### 9.7.3 Other safety parameters

#### Clinical laboratory tests

Descriptive statistics and mean change from baseline to each post-baseline value will be provided for clinical laboratory tests (Day 2 - baseline, and follow up/ET - baseline).

Clinical laboratory values from fasting blood and urine samples will be reviewed for PCS values as assessed by the investigator. Participants with PCS laboratory values will be listed.

#### Vital signs

Descriptive statistics for each scheduled timepoint and for change from baseline to selected timepoints will be provided for vital signs (BP, HR, and oral temperature) and weight. Vital sign results will be reviewed for PCS abnormal values according to predefined criteria, and participants with PCS vital signs will be listed.

#### Electrocardiograms

Descriptive statistics for each scheduled timepoint and for change from baseline to each scheduled timepoint will be provided for each ECG parameter (HR, PR interval, QRS duration, QT, and QTcF). ECG results will be reviewed for PCS abnormal values according to predefined criteria. Participants with PCS ECG values will be listed.

## Psychometric tests and C-SSRS test

Descriptive statistics for each scheduled time point and for change from baseline to each scheduled time point will be provided for each score or sub-score. Mean graphs may also be displayed.

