## 7.4.5 Columbia-Suicide Severity Rating Scale

As this is a central nervous system active compound, the prospective assessment of suicidality is collected using the Columbia-Suicide Severity Rating Scale (C-SSRS) on the days and times noted in the schedule of activities in section 1.3. The C-SSRS is a comprehensive assessment that identifies whether someone is at risk for suicide, assesses the severity and immediacy of that risk, and gauges the level of support that the person needs [12]. The C-SSRS is designed to assess both suicidal behavior and suicidal ideation and consists of 2 questionnaires: one designed for the screening and baseline assessment (covers the participant's lifespan until the baseline visit) and one used during the trial ('Since last visit' questionnaire). A representative example of the C-SSRS that will be used in this trial is provided in [Appendix 5](#).

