### **8.1.2 Baseline (Day -1; confinement period)**

The following procedures will be performed on Day -1 after check-in at the research facility:

- COVID-19 test.
- Questioning for COVID-19 symptoms.
- Confirmation of eligibility for the trial according to the inclusion and exclusion criteria.
- Update of medical history, including intercurrent illness.
- A brief physical examination will be performed.
- Body weight will be measured, and BMI calculated.
- Resting 12-lead ECG will be obtained in a supine position prior to any blood sampling.
- Resting BP, HR, and oral temperature will be measured in a supine position prior to any blood sampling.
- Recording of AEs.
- Update of prior and concomitant medications.
- C-SSRS evaluation (Screening/Baseline version) will be performed.
- Collection of blood samples for:
  - Fasting (at least 6 hours) safety laboratory parameters (chemistry, hematology, and coagulation profile).
- Collection of urine for:
  - Urinalysis.
  - Urine drug screen.
  - Urine pregnancy test (female participants only).
- Alcohol breath test.
- An evening snack will be consumed at approximately 21.30 pm.
- Participants will fast overnight beginning at approximately 23 pm.

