#### **8.1.4 Day 2 (confinement period)**

The following evaluations and procedures will be performed on Day 2:

- A brief physical examination will be performed.
- Pre-breakfast body weight will be measured.
- Resting 12-lead ECG will be obtained in a supine position at 24 hours post dose and prior to any blood sampling.
- Resting BP, HR, and oral temperature will be measured in a supine position at 24 hours post dose and prior to any blood sampling.
- AE assessment by querying with non-leading questions and observation.
- Recording of any concomitant medications.
- Collection of blood samples for:
  - Fasting (6 hours) safety laboratory parameters (chemistry, hematology, and coagulation profile) at 24 hours post dose.
  - Determination of plasma AEF0117 concentration (6 mL) at 24 hours post dose.
  - Determination of plasma concentration of potential metabolites (6 mL) at 24 hours post dose.
- Collection of urine for urinalysis.
- C-SSRS evaluation will be performed (Since Last Visit version).
- Breakfast will be consumed.

When all the above procedures have been performed, participants will be discharged from the research facility.

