### *Disclaimer:*

*This scale is intended to be used by individuals who have received training in its administration. The questions contained in the Columbia-Suicide Severity Rating Scale are suggested probes. Ultimately, the determination of the presence of suicidal ideation or behavior depends on the judgment of the individual administering the scale.*

*Definitions of behavioral suicidal events in this scale are based on those used in The Columbia Suicide History Form, developed by [name] and [name], Conte Center for the Neuroscience of Mental Disorders (CCNMD), New York State Psychiatric Institute, [name]. (Oquendo M. A., Halberstam B. & Mann J. J., Risk factors for suicidal behavior: utility and limitations of research instruments. In M.B. First [Ed.] Standardized Evaluation in Clinical Practice, pp. 103 -130, 2003.)*

*For reprints of the C-SSRS contact [name]., New York State Psychiatric Institute, [name]; inquiries and training requirements contact [contact]*

SUICIDAL IDEATION		
Ask questions 1 and 2. If both are negative, proceed to "Suicidal Behavior" section. If the answer to question 2 is "yes", ask questions 3, 4 and 5. If the answer to question 1 and/or 2 is "yes", complete "Intensity of Ideation" section below.	Lifetime: Time He/She Felt Most Suicidal	Past 6 Months

1. Wish to be Dead            Subject endorses thoughts about a wish to be dead or not alive anymore, or wish to fall asleep and not wake up.  Have you wished you were dead or wished you could go to sleep and not wake up?
 
If yes, describe:
	Yes  No 	Yes  No 

2. Non-Specific Active Suicidal Thoughts            General non-specific thoughts of wanting to end one's life/commit suicide (e.g., "I've thought about killing myself") without thoughts of ways to kill oneself/associated methods, intent, or plan during the assessment period.  Have you actually had any thoughts of killing yourself?
 
If yes, describe:
	Yes  No 	Yes  No 

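### The planned C-SSRS change from baseline subtracts scores with different recall windows, so the change summary and any mean graph of it cannot be interpreted

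*Protocol*

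**What the plan says.** Under the heading for psychometric tests and the C-SSRS, protocol section 9.7.3 plans descriptive statistics at each scheduled time point and then adds that these "for change from baseline to each scheduled time point will be provided for each score or sub-score". It continues: "Mean graphs may also be displayed".

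Section 7.4.5 describes two questionnaires. The first is "one designed for the screening and baseline assessment (covers the participant's lifespan until the baseline visit"). For the visits after dosing the section names a second form, "one used during the trial ('Since last visit' questionnaire"). The visit sections assign them as follows:

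- Day -1 (8.1.2): "C-SSRS evaluation (Screening/Baseline version) will be performed". Screening (8.1.1) uses the same form.
- Day 2 (8.1.4): "C-SSRS evaluation will be performed (Since Last Visit version"). Day 14 or early termination (8.1.6) uses the same form.

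The forms in Appendix 5 agree. The baseline form has two ideation columns, a lifetime column headed "Time He/She Felt Most Suicidal" and a past-6-months column, and a lifetime column for behavior. The follow-up form has a single post-dose column.

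**The concern.** A change from baseline has meaning when both scores measure the same thing over comparable periods. Here the baseline score is a worst-ever or worst-in-six-months recall, and the later score covers days. A participant with remote ideation and nothing after dosing can be scored as improved although nothing in the participant changed.

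Section 7.4.5 justifies the scale by the drug's action on the central nervous system. Its purpose in a trial of this size is to pick up individual emergent cases. A mean of differences between unlike recall periods does not serve that purpose, and a graph of it invites a reading that the data cannot support.

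**Working it through.** The plan states no figure for this analysis, so there is nothing to reproduce. The check compares the recall windows and then asks whether the sign of the mean change can mislead.

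**Recall windows**

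| Visit | Form | Ideation window | Behavior window |
|---|---|---|---|
| Screening, Day -1 | Baseline/Screening | Lifetime; past 6 months | Lifetime |
| Day 2 | Since Last Visit | About 1 to 2 days (from Day -1) | Same |
| Day 14 | Since Last Visit | About 12 days (from Day 2) | Same |

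Neither baseline column matches either follow-up window. Section 9.7.3 does not say which ideation column is subtracted. For behavior only the lifetime column exists.

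The intensity sub-scores have a further gap. The form asks for them only after a positive answer to question 1 or 2. A participant with no history and new ideation therefore has no baseline intensity score to subtract.

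**One participant (assumed scores).** Lifetime type 3, past 6 months 0, new post-dose type 2:

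- against the lifetime column: 2 - 3 = -1
- against the past-6-months column: 2 - 0 = +2

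The same answers give opposite signs depending on the column.

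**One arm (assumed scores).** The planned arm size is 16. Suppose one participant with baseline 0 reports new type 2 ideation. Suppose k others have lifetime ideation of type L and report nothing after dosing. With the lifetime column,

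mean change = (2 - k x L) / 16.

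| k | L | Mean change |
|---|---|---|
| 0 | none | 2/16 = +0.125 |
| 1 | 1 | 1/16 = +0.06 |
| 1 | 2 | 0/16 = 0 |
| 1 | 3 | -1/16 = -0.06 |
| 2 | 2 | -2/16 = -0.125 |
| 2 | 3 | -4/16 = -0.25 |
| 3 | 3 | -7/16 = -0.44 |

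The mean is negative whenever k x L exceeds 2. If the past-6-months column is used and is 0 for everyone, the mean change is +0.125 in every row. A count of participants with any post-dose ideation is 1 of 16 in every row, whichever column is chosen.

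**Eligibility.** Exclusion criterion 7 (section 5.3.2) bars active or recent ideation and an abnormal C-SSRS result. It does not define abnormal. The past-6-months ideation baseline should therefore be about 0. Whether remote lifetime ideation is admitted cannot be settled from the text. If any lifetime positive answer counts as abnormal, every ideation and behavior baseline is 0 and the rows with k of 1 or more cannot arise.

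**The case against.** A reader might infer that the planned output would hide a new case of suicidality, or that it is biased towards improvement for anyone with past ideation. The documents do not support either reading.

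- The same sentence in section 9.7.3 plans statistics at each time point, which subtract nothing. Section 9.3 includes the minimum and maximum for numerical data, participant counts and percentages for categorical data, and a listing of all data. The ideation and behavior items are yes/no, so a new positive answer would appear there.
- In the arm example the planned change table itself has a maximum of +2. In the single-participant example the lifetime change is -1, but the post-dose score of 2 still appears in the visit statistics and the listing.
- The downward pull exists only with the lifetime column, and only if remote lifetime ideation passes exclusion criterion 7.
- Section 7.3.1 asks that clinically significant changes in other safety assessments be reported as adverse events. Its examples do not name the C-SSRS, but they are only examples, so this is a possible second route into the report.
- The C-SSRS is not among the secondary safety endpoints in section 3, and the mean graphs are optional.

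All of this stands, and it limits the consequence. It can also be said that the choice of baseline column belongs in the statistical analysis plan. That is fair, but it does not rescue the analysis: neither column matches the follow-up window, and the protocol has already fixed change from baseline as a method to be elaborated.

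**Conclusion.** The point holds as a minor defect in one secondary safety summary. The protocol prescribes a C-SSRS change score whose two parts cover different recall periods, and it collects no pre-dose score with a matching window. That conclusion rests on the text alone.

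The possible sign reversal is conditional. It needs the lifetime column as baseline and the eligibility of participants with remote lifetime ideation. Under those two assumptions, one other participant with lifetime type 3 in an arm of 16 is enough to move the mean from +0.125 to -0.06. The scores and counts are illustrations, since the documents give none. With the past-6-months column the effect should not occur for ideation.

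An emergent case would remain visible in the visit statistics and listings. The fault is confined to the change-from-baseline summary and any mean graph of it, and the primary pharmacokinetic analysis is untouched.

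**What to change.** In section 9.7.3:

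- Delete change from baseline and mean graphs for the C-SSRS.
- Report, by group and visit, the number of participants with any post-dose suicidal ideation (by type 1 to 5) or behavior.
- List all positive answers, with each participant's pre-dose lifetime and past-6-months responses alongside as history.
- If a shift table is wanted, name the baseline window and label the table as a comparison with history, not as change. A shift table against an unnamed baseline would repeat the mismatch.
- Delete the reference to psychometric tests, since the schedule contains none other than the C-SSRS.

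The cost is one rewritten paragraph and a simpler table. No new data or visits are needed.

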## 9.8 Participant withdrawals and missing data

All data will be included and used as recorded. Specific participants and/or data may be excluded from the PK analysis as described in [9.2.3](#).

## 9.9 Interim analyses

Not applicable.

## 9.10 Other analyses

### 9.10.1 Subgroup analyses

Not applicable.

### 9.10.2 Exploratory analyses

If the data allow, a PK analysis will consist of a non-compartmental evaluation of the metabolite plasma concentration-time profiles to determine PK parameters using a validated program. PK parameters will be tabulated and plots of plasma concentration as a function of time provided for the 2 conditions (fed/fasting). The results of the explorative measures will be reported separately.

# 10 ETHICAL, LEGAL AND ADMINISTRATIVE ASPECTS

## 10.1 Statement of compliance

The investigator is responsible for ensuring that the trial will be conducted in adherence with the clinical trial protocol, Good Clinical Practices as defined in Title 21 of the US Code of Federal Regulations Parts 50, 54, 56, 312 and Part 11 as well as ICH E6: Guideline for Good Clinical Practice (ICH GCP) [\[13\]](#) and applicable regulatory requirements (<http://www.fda.gov/cder/guidance/index.htm>).

The investigator is responsible for ensuring the accuracy and completeness of all research records, the accountability of the trial drug, and the conduct of clinical and laboratory evaluations as outlined in this protocol.

It is the responsibility of the investigator to assure that all aspects of the ethics and regulatory review are conducted in accordance with the Declaration of Helsinki as described in the ICH GCP, and/or local laws, whichever provides the greatest level of protection for the trial participants.

## 10.2 Institutional review board/ethics committee

The investigator must ensure that the protocol and any information provided to the participant such as written ICFs, written participant information, and participant recruitment procedures (e.g., advertisements) will be reviewed and approved by a qualified IRB/EC to initiation of the trial. In the event of amendments, approval of the updated documents must be obtained before they are implemented.

The investigator and sponsor or designee, will make all attempts to ensure that the IRB/EC is constituted and operates in accordance with ICH GCP, federal, and any local regulations.

All IRB/EC approvals must be dated and signed by the IRB/EC chairperson or designee and must identify the IRB/EC by name and address, the clinical protocol by title and/or protocol number, the date approval or favorable opinion was granted for the clinical trial, as well as the list of the committee members.

Prior to initiation of the trial, the sponsor must ensure that all ethical and legal requirements have been met and must receive documentation of the IRB/EC approval. No drug will be released to the site to dose a trial participant until written IRB/EC approval/favorable opinion has been received by the sponsor or designee.

Investigators must submit progress reports to the IRB/EC in accordance with the IRB/EC requirements. Continuing review and re-approval of the clinical trial must be performed at least annually or more often if specified by the IRB/EC. Copies of progress reports and re-approvals must be sent to the sponsor.

The sponsor and investigator will comply with all country-specific and local regulatory requirements relating to safety reporting to the regulatory authorities and IRBs/ECs.

The investigator, as part of the records retention requirements for the trial, must maintain documentation of all submissions, correspondence, and approvals to and from the IRB.

The investigator will notify the IRB when enrollment stops and when the analysis of data is completed.

## 10.3 Changes to the protocol

### 10.3.1 Protocol amendments

Any important changes to the protocol (i.e., changes that significantly affect participant safety or the scope or scientific quality of the trial), except those to remove an apparent immediate hazard to the trial participants, must be made in a substantial protocol amendment that must be reviewed and approved by the sponsor or designee, and the IRB/EC and regulatory authorities that approved the trial prior to participants being enrolled into the amended protocol.

Substantial amendments to the protocol must be reviewed and approved following the same requirements and conditions as for the original protocol. The investigator must send a copy of the approval letter from the IRB/EC to the sponsor and retain the original in the site trial regulatory file.

The sponsor may make administrative changes (i.e., changes that do not significantly affect participant safety or the scope or scientific quality of the trial) without any further approvals (non-substantial/administrative amendment).

All amendments will be distributed to all protocol recipients.

### **10.3.2 Protocol deviations**

A protocol deviation is any noncompliance with the clinical trial protocol or with ICH GCP requirements. Deviations from the protocol should be avoided, except if necessary to remove an immediate hazard to the participants. Prospective approval of protocol deviations (also known as protocol waivers or exemptions) is not permitted.

All protocol deviations will be recorded and qualified as critical, major, or minor. Critical and major deviations will be summarized in the CTR.

Major and critical deviations must be reported to the sponsor and to the IRB/EC in accordance with the IRB/EC requirements. During the trial the trial monitor must notify the sponsor of subjects found not to have met eligibility criteria. The medical monitor in collaboration with the investigator will determine if the participant should be withdrawn from the trial.

The IRB/EC that granted original approval, or the IRB/EC currently responsible for overseeing the conduct of the trial, must be notified of all changes in and deviations from the protocol that may increase risk to the participants, and/or that may adversely affect the rights of the participant or the validity of the investigation.

## **10.4 Participant recruitment, consent, and participation**

### **10.4.1 Recruitment strategies**

Recruitment for this trial will occur primarily through advertisements in local newspapers and online, and by word of mouth. Interested individuals will respond to advertisements by calling the research facility for information about the trial.

Participants will be financially compensated for their time and traveling costs, subject to IRB/EC approval of conditions.

### **10.4.2 Written participant information and informed consent form**

Preparation of the written participant information and ICF is the responsibility of the investigator and the sponsor or designee. The document must include all elements required by ICH GCP and applicable regulatory requirements, including 21 Code of Federal Regulations § 50, and must adhere to the ethical principles that have their origin in the Declaration of Helsinki [14]. The document must be written in a language understandable to the participant and must specify who informed the participant.

The sponsor or designee must review and approve all changes to the trial-specific ICF. Any changes requested by the IRB/EC must also be approved by the sponsor or designee. The final IRB/EC-approved ICF must be provided to the sponsor or designee. Revisions to the ICF required

during the trial must be approved by the sponsor or designee, and a copy of the revised ICF provided to the sponsor or designee.

The ICF must include a statement that the sponsor or designee and regulatory authorities have direct access to participant records and that pseudonymized data will be securely transferred to the sponsor/third parties. Prior to the beginning of the trial, the investigator must obtain the IRB/ECs written approval/favorable opinion of the written ICF and any other information to be provided to the participants.

#### **10.4.3 Informed consent process**

The investigator will not undertake any measures specifically required only for the clinical trial until valid consent to participate in the trial has been obtained.

The participants must be informed about the nature, scope, and possible consequences of the trial in a form understandable to them. The written participant information that includes information about the trial and the ICF will be given to the participant.

Where required by local law, the person who informs the participant must be a physician. After the investigator or designee is assured that the participant understands the commitments of participating in the trial, the participant will be asked to sign and date the ICF.

A copy of the fully signed and dated consent documents must be given to the participant. The original signed consent documents will be retained by the investigator at the trial site. All active participants will sign an updated ICF if revisions are made to the ICF during the trial.

The investigator may inform the participant's primary physician about the participant's participation in the trial if the participant has a primary physician and if the participant agrees to the primary physician being informed.

#### **10.4.4 Trial participation card**

The subjects will be provided with a trial participation card including the following information:

- That he/she is participating in a clinical trial, including the trial code.
- That he/she is treated with an investigational drug.
- The name and phone number of the contact person at the site.

The participants will be asked to keep the trial participation card in their possession during the trial and to return it to the site at the follow-up visit.

